# Introduction

Proper airway management (AM) is an essential goal for anesthesia providers. Poor airway assessment and planning contributed to unfortunate airway outcomes. Airway management skills are indispensable for an emergency physician. Unrecognized airway accidents such as esophageal intubation tend to occur more in emergency settings  where it is reported as 6%-16%.

The inability to successfully intubate a pharmacologically paralyzed patient can be a disastrous situation. Although patients who are potentially difficult to intubate can often be predicted clinically, this method does not provide complete assurance, providing a requirement to consider other methods.  Also, confirmation of proper tracheal intubation could be performed primarily by direct laryngoscopy, auscultation of Gurgling sounds in the epigastric region, lung auscultation, observation of water vapor on endotracheal tube wall, using esophageal detector device, CXR and ETCO2 (end-tidal CO2 pressure) that each of the above-mentioned methods have its own limitations .

Obesity is a well-known independent predictor of difficult intubation, but increased body mass index poorly predicts difficult laryngoscopy.

A large neck circumference is among the suggested predictors of difficult intubation, especially in obese patients and it has been reported to predict difficult laryngoscopy. Neck circumference, though, does not indicate the amount of soft tissue at various topographic regions within the neck. Distribution of fat in different neck areas may provide better information than neck circumference. 

Ultrasound (US) offers a number of attractive advantages compared with competitive imaging techniques or endoscopy for imaging critically ill patients. It is widely available, portable, repeatable, relatively inexpensive, pain-free, and safe.

Although the earliest reports dealing with US applications in clinical medicine include the description of soft-tissue imaging of the pretracheal structures and anterior Ultrasound (US) evaluation of the airway is found to be an excellent tool in different medical settings including the operating room, intensive care unit and in the emergency department (ER). The utility of the US in the airway management is not limited to the upper airway assessment; it has been also used to evaluate the lower airway, lungs and pleura .

## **Aim of the work**

The aim of the study is to determine whether preoperative ultrasound assessment of the upper airway can predict difficult laryngoscopy in emergency surgical obese patients , by analysis correlations between ultrasound measurements of anterior cervical soft in the upper airway, and the Cormack–Lehane grade. And evaluate its role in confirming the endotracheal placement

The secondary objective was to determine whether clinical screening tests are independent predictors of difficult airway.

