### **Will evaluate the following variables:**

- 1- Mallampati score
- 2- Neck mobility (flexion/extension degrees from midline),
- 3- Upper lip bite test,
- 4- Temporomandibular joint mobility assessed by mouth-opening and forward movement of the jaw and the ability to protrude the lower teeth further than the upper teeth;
- 5- . A flexible ruler will be used to measure airway parameters, mouth opening (cm), thyromental distance (cm), sternomental distance

(cm), hyomental distance (cm) and neck circumference (cm) at the level of the thyroid cartilage.

The thicknesses of the anterior neck soft tissues will be measured with a portable ultrasound machine). A 6 to 13 MHz high frequency curvilinear ultrasound transducer was used for ultrasound scanning. Patients will be explained about the ultrasonography procedure and positioned in supine with the head in a neutral position. Ultrasonography with the probe placed in the transverse axis, craniocaudal sagittal scan, submental region of the neck. The distances will be measured at five levels (hyoid bone, epiglottis, cricothyroid membrane, thyroid isthmus and suprasternal notch) with normal and extended neck position in the median axis.

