### **Intraoperative:**

After 5 min. preoxygenation, anesthesia will be induced with fentanyl (1-2  $\mu$ g/kg), propofol (2-4 mg/kg) and succinylcholine (1 mg/kg). with patient's head in sniffing position on a standard operating room pillow at a height of 5 cm., an anesthesiologist who is unaware of the ultrasound results will perform laryngoscopy with a Macintosh

No. 3 blade and insert an endotracheal tube of the proper size.

Laryngoscopic view will be graded according to the method described by Cormack and Lehane as grade 1 (full view of the glottis), grade 2 (glottis partly exposed, anterior commissure not seen), grade 3 (only epiglottis seen), or grade 4 (epiglottis not seen). No external laryngeal pressure will be applied while reporting the laryngeal view.

If intubation failed after three attempts, the study ended and alternative methods for airway placement will be pursued.

To confirm endotracheal intubation, tracheal ultrasound during endotracheal intubation (ETI) will be performed. Ultrasound probe will be set on the outside of larynx and glottis during intubation and tube passage through trachea is checked.

Statistical analysis; Our results will be statistically analyzed and expressed as tables and figures.

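### The main aim is to predict difficult laryngoscopy, but the means named is correlation with the four-level Cormack–Lehane grade, which does not fix predictive accuracy

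*Protocol*

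**What the plan says.** The Protocol, under Aim of the work, sets out to "determine whether preoperative ultrasound assessment of the upper airway can predict difficult laryngoscopy in emergency surgical obese patients". The sentence goes on to give the method: "by analysis correlations between ultrasound measurements of anterior cervical soft in the upper airway, and the Cormack–Lehane grade". No type of coefficient is named.

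Under Will evaluate the following variables, the ultrasound data are continuous distances: "The distances will be measured at five levels (hyoid bone, epiglottis, cricothyroid membrane, thyroid isthmus and suprasternal notch) with normal and extended neck position". Five levels in two positions make 5 × 2 = 10 measurements per patient.

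Under Intraoperative, the outcome is an ordered scale: "grade 1 (full view of the glottis), grade 2 (glottis partly exposed, anterior commissure not seen), grade 3 (only epiglottis seen", and then grade 4. The protocol describes each grade but does not tie any of them to difficult laryngoscopy. The only other statistical text is one general sentence: "Our results will be statistically analyzed and expressed as tables and figures".

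**The concern.** Whether ultrasound predicts difficult laryngoscopy is a question about separating two groups of patients: those who turn out difficult and those who do not. The useful answer is how many difficult cases a measurement catches and how many easy ones it flags wrongly. The Introduction frames the need in that way, since it describes failure to intubate a paralysed patient as potentially disastrous and clinical prediction as incomplete.

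A correlation across four grades answers a neighbouring question: do thicker tissues go with worse views in general? Part of that coefficient comes from the grade 1 versus 2 contrast, which says nothing about difficulty if the cut lies between grades 2 and 3. A study could therefore report a clear correlation and still leave open how well ultrasound identifies the patients who matter.

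**Working it through.** The protocol states no correlation, sample size or accuracy figure, so there is nothing of its own to reproduce. The check is whether one correlation value pins down predictive accuracy.

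**Assumed inputs (none is in the protocol).** Spearman's coefficient, set at 0.335. A normally distributed measurement with SD 1 within each grade. Difficult = grades 3–4. Three mixes of grades 1/2/3/4: 50/30/17/3% (20% difficult), 40/30/25/5% (30%) and 60/30/8/2% (10%).

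**Formulas.** With grade shares p_i and grade means μ_i:
- Spearman's coefficient is the correlation of F(X) with the grade midranks, where F is the distribution function of the whole mixture. The means are scaled until it equals 0.335.
- AUC = Σ e_i d_j Φ((μ_j − μ_i)/√2), with i over grades 1–2, j over grades 3–4, and e, d the shares within the easy and difficult groups.
- The cut-off c solves Σ e_i Φ(c − μ_i) = 0.80. Sensitivity = Σ d_j [1 − Φ(c − μ_j)].

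**Worked case: 20% difficult, equal step per grade.** The means are 0, 0.438, 0.877, 1.315; e = (0.625, 0.375); d = (0.85, 0.15).
- AUC = 0.625 × (0.85 × 0.732 + 0.15 × 0.824) + 0.375 × (0.85 × 0.622 + 0.15 × 0.732) = 0.466 + 0.239 ≈ 0.71.
- c = 1.025, since 0.625 × 0.847 + 0.375 × 0.721 = 0.80.
- Sensitivity = 0.85 × 0.441 + 0.15 × 0.614 = 0.467, or 47%.

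**Same correlation, other patterns of means.** Each cell gives AUC and sensitivity at 80% specificity.

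| Pattern over grades 1–4 | 10% difficult | 20% difficult | 30% difficult |
|---|---|---|---|
| Grades 2–4 equal (limit) | 0.63, 35% | 0.63, 34% | 0.63, 33% |
| Two thirds of the rise by grade 2 | 0.70, 44% | 0.67, 41% | 0.66, 40% |
| Equal steps | 0.75, 55% | 0.71, 47% | 0.68, 43% |
| One quarter of the rise by grade 2 | 0.84, 70% | 0.75, 55% | 0.72, 49% |
| Grades 1–2 equal (limit) | not attainable (maximum 0.310) | 0.82, 68% | 0.75, 55% |

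The AUC runs from about 0.63 to 0.84 and the sensitivity from about 33% to 70%, all at a correlation of 0.335. The two rows marked as limits are bounds, not expected patterns.

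**Why it varies.** The covariance behind the coefficient is a sum over pairs of grades. Each pair's difference in mean measurement rank is weighted by p_i p_j × (midrank difference). In the 20% mix the grade 1 versus 2 pair has weight 0.50 × 0.30 × (0.65 − 0.25) = 0.060 out of 0.1405 over all six pairs, or 43%. In the 30% and 10% mixes it is 28% and 64%. A large part of the coefficient can therefore come from a contrast wholly within the easy group.

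**Precision of the replacement.** The Hanley–McNeil variance is [A(1−A) + (n₁−1)(Q₁−A²) + (n₀−1)(Q₂−A²)]/(n₁n₀), with Q₁ = A/(2−A) and Q₂ = 2A²/(1+A). For A = 0.70 and 20% difficult:
- n = 50 (10 v 40): SE 0.100, so 0.70 ± 1.96 × 0.100 = 0.50 to 0.90.
- n = 100 (20 v 80): SE 0.071, so 0.56 to 0.84.

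Both sample sizes are assumed.

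**The case against.** The best reply is that the clause is loose wording in an aims paragraph. It names no coefficient or test and could be read as simply relating the measurements to the grade. A statistical analysis plan, not shown here, could carry that out as an ROC analysis. That disposes of any complaint resting on absence alone: a missing accuracy measure, or a missing definition of difficult, is no finding in itself. It does not dispose of this point, because the protocol goes beyond silence and names a means for its main aim. Whatever a later plan adds, that sentence would still need correcting.

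It is also fair to say that some correlations do determine accuracy: with a two-level outcome, the rank-biserial correlation equals 2 × AUC − 1. The point is confined to a rank correlation over four levels.

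Two stronger readings are tempting, and the documents support neither.
- A reader might infer that the correlation is very likely to reach significance while about half of the difficult cases are missed. That needs a correlation, sample size, alpha, grade pattern and chosen specificity, none of which the protocol states. Under one of the assumed patterns at the same correlation, only 30% are missed (100% − 70%).
- A reader might infer that the protocol rules out accuracy analysis or that the correlation is worthless. Its general sentence on statistics excludes nothing, and association with laryngeal view is relevant evidence.

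**Conclusion.** The point holds in limited form. The analysis named for the main aim is relevant but insufficient: it shows association with the laryngeal view and leaves sensitivity, specificity and AUC for difficult laryngoscopy open. That conclusion follows from the four-level scale and needs no assumed figure. The ranges in the table show how open the answer is, but they rest on the assumed correlation, distribution, grade mixes and cut at grades 3–4, and they are illustrative only.

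This should be fixed, but it does not undermine the study. The distances and all four grades are already to be recorded, so the right analysis remains available if it is fixed in time.

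**What to change.** Amend the clause on correlations under Aim of the work. Possible wording:

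*Difficult laryngoscopy is defined before enrolment as a stated cut of the Cormack–Lehane grade (for example grades 3–4 versus 1–2). The main analysis is the AUC with 95% CI for one pre-named ultrasound measurement (level and neck position); the other measurements are secondary. Sensitivity and specificity are reported with 95% CIs. If the cut-off is chosen from the data, these estimates are corrected for optimism, for example by bootstrap. Correlations with the four-level grade are descriptive.*

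Naming one of the ten measurements in advance matters, since picking the best performer afterwards would flatter the result. The optimism correction applies to the estimated sensitivity and specificity, not to the cut-off itself. The secondary objective concerns difficult airway, which may be a wider outcome than the view grade, so it should stay out of this change.

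The cost is wording only, with no new data. There are two downsides. Dichotomising discards some information, which the descriptive correlations partly retain. The AUC interval will also be wide if the study is small, as the intervals at 50 and 100 patients show.

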### **Inclusion criteria:**

Adult obese patients (BMI>35) of both sex aged from 18 to 60 years undergoing urgent surgeries under general anesthesia with tracheal intubation.

### **Exclusion criteria:**

. Patients with removable upper dentures, upper airway pathology, cervical spine fractures, full stomach, maxillofacial trauma or unstable patients and pregnant women will be excluded from the study.

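### Is the aim, set for emergency surgical obese patients, contradicted by exclusions that remove full-stomach and unstable patients?

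*Protocol*

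**What the plan says.** The section Aim of the work puts the question in one sentence: whether ultrasound of the upper airway "can predict difficult laryngoscopy in emergency surgical obese patients", by correlating anterior neck measurements with the Cormack-Lehane grade. It adds a second purpose, confirming tube placement. It mentions neither stability, fasting status nor age.

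The Inclusion criteria come next: "Adult obese patients (BMI>35) of both sex aged from 18 to 60 years undergoing urgent surgeries under general anesthesia with tracheal intubation".

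The Exclusion criteria follow. After removable upper dentures, the list continues: "upper airway pathology, cervical spine fractures, full stomach, maxillofacial trauma or unstable patients and pregnant women will be excluded from the study".

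Two remarks in the Introduction bear on the point. One says "Unrecognized airway accidents such as esophageal intubation tend to occur more in emergency settings", with a reported frequency of 6% to 16%. The other says that ultrasound "offers a number of attractive advantages compared with competitive imaging techniques or endoscopy for imaging critically ill patients".

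The section listing the variables to be evaluated has the distances measured "with normal and extended neck position in the median axis". It also calls for neck mobility, mouth opening, jaw movement and the upper lip bite test.

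**The concern.** Read in order, the document appears to argue for one population and study another. The Introduction draws on emergency airway accidents and on imaging of the critically ill. The aim takes up the word emergency without a qualifier. The exclusions then remove unstable patients and those with a full stomach. The inclusion criteria also speak of urgent rather than emergency surgery, which blurs the target a little more.

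In a study of prediction and of tube confirmation, the population in which performance is estimated governs where the result can be used. If the aim were taken at face value, a reader might apply the findings to full-stomach or unstable patients, for whom the study will hold no data. That would concern both the relation between ultrasound measurements and laryngoscopic grade and the use of ultrasound to confirm placement.

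**Working it through.** The protocol gives no figure on this point to reproduce, and no formula applies. The check sets the sections side by side.

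1. **Do the sections conflict?** The aim names obese patients having emergency surgery. The criteria take adults aged 18 to 60 with BMI above 35 having urgent surgery, less the listed exclusions. Reading urgent surgery as falling within emergency surgery, every enrolled patient belongs to the population named in the aim. The enrolled group is a subset of it. A conflict would need enrolled patients outside the aim, or two sections giving incompatible rules on the same patient. Neither occurs.

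2. **How many exclusions are in question?** There are seven: removable upper dentures, upper airway pathology, cervical spine fractures, full stomach, maxillofacial trauma, instability and pregnancy. The aim repeats none of them, but a one-sentence aim rarely does, so a count of 0 out of 7 says little. Four could be called typical of emergencies: cervical spine fractures, maxillofacial trauma, full stomach and instability. Two of these are consistent with the study's own procedures:
   - Cervical spine fractures: the scan uses an extended neck, and neck mobility is examined.
   - Maxillofacial trauma: mouth opening, jaw protrusion and the upper lip bite test are measured.

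   That leaves 4 − 2 = 2, full stomach and instability.

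3. **Does the Introduction define the population?** The remark on critically ill patients is a general statement about ultrasound, followed by its portability, cost and safety. The same section describes airway ultrasound in the operating room, the intensive care unit and the emergency department, and it opens with anesthesia providers. The sentence on emergency settings concerns where misplaced tubes go unrecognized; it mentions neither full stomach nor instability. These passages give reasons for interest in the method. They do not say whom this study is about.

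4. **Are results within the study distorted?** No exclusion is defined by the ultrasound reading or by the Cormack-Lehane grade. The exclusions determine whom the estimates describe; they do not bias those estimates for the enrolled group.

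5. **Does the protocol over-claim?** It contains no conclusion and no statement that results apply to excluded patients. An over-broad claim would have to be made later, in a report, against eligibility criteria that are already explicit.

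6. **What would a change achieve?** Writing the eligibility criteria into the aim would leave enrolment, measurements, analysis and results exactly as they are.

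**The case for a change.** The strongest case for a defect is that this goes beyond routine narrowing. Omitting dentures or pregnancy from the aim would trouble nobody. Unstable patients, however, plainly overlap with the critically ill whom the Introduction invokes, and the aim keeps the word emergency unqualified. The protocol never says that its answer is meant only for stable patients without a full stomach. The aim and the eligibility criteria both stand in this document, so the matter cannot be left to an analysis plan, and the wording could be tightened at no cost.

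Part of this stands. The aim is broader in wording than the enrolled group, and the study will provide no information on full-stomach or unstable patients. Anyone who uses the results should keep to the population that the criteria describe.

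The step from there to a defect does not stand. The limitation can be read from the criteria immediately below the aim. The overlap between the Introduction's background and the excluded patients creates no rule that the criteria break. Nor does the protocol indicate whether ultrasound would perform better, worse or the same in those patients, so no particular error can be shown to follow. That the wording is cheap to tighten does not make it wrong.

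**Conclusion.** The concern does not hold. A short aim names the population in general terms, and the inclusion and exclusion criteria define it explicitly straight afterwards. Enrolling a defined subset is ordinary narrowing by eligibility.

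The size of the gap cannot be given: the protocol states no frequency for any exclusion and no expected rate of difficult laryngoscopy, and it does not indicate the direction of any difference. What remains is two exclusions out of seven that limit applicability, both openly stated, and no bias within the enrolled group.

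The conclusion rests on two assumptions: that urgent surgery in the inclusion criteria falls within emergency surgery in the aim, and that the eventual report keeps its conclusions to the patients enrolled. Whether the exclusions are clinically appropriate is not judged here.

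### The cervical-spine exclusion covers fractures only, so a stable patient with a suspected or uncleared neck injury is eligible for a research scan with the neck extended

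*Protocol*

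**What the plan says.** The Protocol's Inclusion criteria take adults aged 18 to 60 with BMI above 35 "undergoing urgent surgeries under general anesthesia with tracheal intubation". The Exclusion criteria remove, among others, patients with "upper airway pathology, cervical spine fractures, full stomach, maxillofacial trauma or unstable patients"; removable upper dentures and pregnancy are also listed.

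The section on variables to be evaluated lists "Neck mobility (flexion/extension degrees from midline" as a bedside test. For ultrasound, the patient is "positioned in supine with the head in a neutral position", and distances at five levels are then taken "with normal and extended neck position in the median axis". Neither the mobility test nor the extended scan carries an exception, and no check of the neck is required first.

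Under Intraoperative, every patient has the "head in sniffing position on a standard operating room pillow", and the laryngoscopist is blinded to the ultrasound findings. The Aim of the work uses the ultrasound distances for the primary question. The bedside tests serve a secondary one: to "determine whether clinical screening tests are independent predictors of difficult airway".

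**The concern.** An eligibility criterion that protects patients from a study procedure should be as wide as the risk the procedure carries. Here the procedure is neck extension and the criterion is an established fracture. A neck injury may be suspected, not yet imaged, or not involve bone. Such a patient has no diagnosed fracture and so is not caught.

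Two things are at stake. The first is safety: a movement made for measurement could be applied to a neck whose condition is not known. The second is completeness of data. In practice the examining anesthesiologist may well decline to extend such a neck. The extended-position distances are then missing, for a reason that may be related to how difficult laryngoscopy turns out to be, and the Protocol says nothing about how to record this.

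**Working it through.** No sample size, rate or power figure enters this point, so the check sets the sections side by side.

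1. **Can injured patients enter?** The Inclusion criteria say urgent surgery and do not rule out trauma. The exclusions name cervical fractures and maxillofacial trauma, so the Protocol itself expects injured patients to be screened.

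2. **Which exclusions could catch a suspected or uncleared neck injury?**
   - Cervical spine fracture: only if a fracture is established.
   - Maxillofacial trauma: only if the face is also injured.
   - Unstable patients: the term is undefined and stands in a general list apart from the cervical item. It does not clearly refer to the spine, and a patient can be stable in the general sense with an uncleared neck.
   - Full stomach: removes some acute trauma cases, but for a reason unrelated to the neck.

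   None covers a patient who is stable, fasted, free of facial injury, and has a suspected or uncleared neck.

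3. **What is done to that patient?** Three items involve neck position or movement:
   - the flexion/extension test, which may also be part of an ordinary airway examination; the Protocol does not say which tests are routine;
   - the ultrasound scan in extension, which serves the study question and cannot inform the blinded laryngoscopist;
   - the head position for laryngoscopy, which belongs to the anesthetic itself.

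   Only the second is plainly there for research.

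4. **How much of the data depends on extension?** Taking one distance per level and position, 5 levels × 2 positions = 10 distances, of which 5 need the neck extended, or 5/10 = half. The other five, in the neutral position, do not depend on it. This count describes the layout of the measurements. It does not measure risk or bias.

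5. **Is the scan position itself clear?** The text places the head in neutral and then asks for both normal and extended positions. The natural reading is that neutral is the starting position and the same as normal, but the Protocol does not say so.

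6. **How many patients?** No trauma share, screening figure or sample size is given. Any percentage would be a guess, so none is offered.

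**The case against.** The strongest reply is that nothing here is contradictory: both sections can be followed, and the patient at issue is hypothetical. To be affected, someone must be injured, stable, fasted, without facial trauma, within the age and BMI limits, and have an uncleared neck. An anesthesiologist takes a history and examines each patient before surgery, and would probably not extend such a neck.

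Much of this stands. The group is likely to be small, and the point concerns a gap in eligibility, not an impossible instruction. Clinical judgement, however, would protect the patient only by departing from the Protocol as written, and the Protocol has no place to record that departure.

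A reader might infer more than the text supports:
- *That fracture is the only relevant exclusion.* It is the only cervical-spine one; other items remove some injured patients.
- *That all the neck movement is study-only.* This fits the extended scan. It is not established for the mobility test.
- *That mobility values will be missing in stiff necks.* A neck that cannot extend gives a low angle, which is a valid result and what the test is meant to detect. The value is missing only if the test is not done.
- *That the primary aim fails.* The neutral-position distances are unaffected.

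**Conclusion.** The point holds as a mismatch between the neck-related exclusion and the neck movements required. As written, a stable urgent-surgery patient with a suspected or uncleared neck injury and no facial trauma is eligible for neck extension for research. Half of the ultrasound distances are taken in that position, assuming one distance per level and position.

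The conclusion rests on two readings: that unstable does not mean an unstable or uncleared spine, and that the extended scan is not part of routine care. The Protocol supports the second through the blinding of the laryngoscopist; on the first it is silent. The frequency is unknown, and neither harm nor bias has been shown. The change is worth making because it is cheap and concerns a procedure done for research.

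**What to change.** Reconcile the Exclusion criteria with the section on variables to be evaluated, so that the neck-related exclusion matches the neck movements the study asks for. There are two routes, and the exact criterion is for the investigators to set:

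- widen the cervical item beyond established fracture, for example to known or suspected cervical spine injury; or
- keep such patients, limit them to the neutral-position scan, and record the extended-position values as not done for that reason, so that the number and cause of missing values can be reported.

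In the same edit, state whether neutral and normal name one scan position, and whether the mobility test is subject to the same limit.

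The cost is about one line of text. With the first route a few injured patients become ineligible; with the second a few lack extended-position values. The wording should not be so broad that it removes patients whose necks are merely stiff. They belong in a study of difficult laryngoscopy, and their low mobility value should be kept as valid data.
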